## 6.2.2 Site Reporting of Adverse Events

The study was designed to capture real world data regarding the clinical use of the FlowTriever System and other high-risk PE treatments. The study follows guidelines for Instructions for Use and physician discretion for PE treatment.

This is a data collection study only; there is nothing investigational or experimental in the subject's medical treatment and the subject will be treated per standard of care. **Therefore, the study will only capture AEs related to the subject's PE condition and treatment.** Reportable AEs include all events considered in the safety analyses, all thrombus removal therapy/device- and/or procedure-related AEs, as well as events resulting in death. The AEs will be captured on the AE CRF and should include, wherever possible, severity, duration, outcome, the Investigator's description the event, and its relationship to the thrombus removal therapy/device, to the thrombus removal procedure or any subsequent procedures, or to a thrombolytic agent or anticoagulant.

- Non-serious reportable AEs are to be submitted via the electronic data capture system (EDC) in a timely fashion.
- Reportable SAEs must be reported to the Sponsor within 5 business days of the Investigator's knowledge of the event. The event is reported in the EDC.

## 6.3 CLINICAL EVENTS COMMITTEE (CEC)

A Clinical Events Committed (CEC) will be utilized in this study for the purposes of adjudicating the primary and secondary endpoints. Site-reported safety and outcome data will be provided to the CEC for review and adjudication of the following items for all FlowTriever and Context Arm subjects enrolled in the study:

- Classification as a Serious Adverse Event (SAE)
- Determination of relatedness
- Assessment of severity
- Assessment of endpoint criteria

Adjudication will be conducted according to the FLAME CEC Charter.

(Note that the primary endpoint will only be analyzed for subjects in the FlowTriever Arm of the study, but the CEC will adjudicate events for subjects enrolled in the Context Arm of the study as well)

## 6.4 PROTOCOL MODIFICATIONS

No changes from the final approved study protocol will be initiated at the site-level without the IRB's prior written approval of the amendment. Site Principal Investigators will acknowledge any protocol amendments by signing the associated Protocol Signature Page.

## 6.5 PROTOCOL DEVIATIONS

A protocol deviation is a divergence or non-adherence from the protocol-specific study procedures. Protocol deviations should be recorded for all assessments not collected, and issues related to eligibility criteria.

Protocol deviations should be recorded in the study record and entered into the study database as soon as possible to ensure Sponsor oversite of the conduct of the study along with implementation of any corrective actions as necessary.

## 6.6 TRAINING FOR STUDY PERSONNEL

The Investigator is responsible for giving information about the study to all staff members involved in the study or in any element of subject management, both before starting the study procedures and during the study; for example, when new staff are involved. The Investigator must ensure that all study staff members are qualified by education, experience, and training to perform their specific responsibilities.

The Sponsor or designee is responsible for explaining the protocol to all study staff, including the Investigator, and for ensuring their compliance with the protocol throughout the study. Additional information will be made available during the study when new staff become involved in the study, and as otherwise agreed upon with either the Investigator or the Sponsor.

## 6.6.1 Physician Device Training

Each physician selected to participate in this trial who will be enrolling in the FlowTriever Arm will be required to have experience treating pulmonary embolism using the FlowTriever device.

## 6.6.2 Site Initiation and Addition of Site Personnel

A Site Initiation Visit (SIV) will be conducted by the Sponsor or designee, either in-person or via teleconference to ensure proper training of the Investigator and study staff members prior to participation in the FLAME study. The SIV will cover training to the study protocol and data collection, as well as to any applicable regulatory requirements, and will be documented in the study record. Additional site personnel added to the study after the SIV will be required to undergo protocol training, to be performed by the Sponsor, or designee, and documented in the study record.

## 6.7 SITE MONITORING VISITS

Interim monitoring visits will be conducted by the Sponsor or designee in-person or remotely to ensure compliance with the protocol, and other written instructions and regulatory guidelines according to the study-specific monitoring plan.

The main responsibilities of the monitor are to ensure adherence to the protocol and to verify all data are correctly and completely recorded. The Investigator and assisting staff must agree to cooperate with the study monitor to resolve any study-related problems, errors, or possible misunderstandings concerning the findings detected during these monitoring visits or data review.

## 6.8 STUDY TERMINATION

The Sponsor and applicable regulatory authorities have the right to terminate the entire study or study activities at an individual site at any time. The circumstances which may warrant study termination include, but are not limited to:

- As a result of the pre-specified Interim Analysis, or
- Increased incidence of adverse experiences and/or the severity of such, suggestive of a potential, device-related health hazard, or
- Insufficient subject enrollment rates, or
- Recurrent protocol deviations or other non-compliances, or
- Inaccurate, incomplete, and/or untimely data recording on a recurrent basis, or
- Lack of cooperation with monitoring visits (e.g., failure to adequately prepare for visits, address action items from one visit to the next, or provide access to medical records)

## 6.9 SITE CLOSE-OUT VISITS

Close-out visits will be conducted by the Sponsor or designee in-person or remotely to ensure compliance with the protocol, and other written instructions and regulatory guidelines.

The close-out visit will be conducted when all subjects at the site have completed the study-specific follow-up, or after early termination as described in **Section 6.8**.

## 6.10 DATA COLLECTION AND MANAGEMENT

The Sponsor and/or designee will be responsible for the processing and quality control of the data. All source data, eCRFs, copies of protocols and protocol amendments, correspondence, and other essential documents must be retained for a period of at least 2 years after the completion, closure, or termination of the study.

No study document or image will be destroyed without prior written agreement between the Sponsor and the Investigator. Should the Investigator wish to assign the study records to another party or move them to another location, advance written notice must be given to the Sponsor.

## 6.10.1 Site Data Collection and Electronic Data Capture (EDC)

The Investigator may keep a separate subject identification list showing enrollment numbers, names, and dates of birth to provide a local key for unambiguous identification of each subject included in the study. This list will not be collected by the Sponsor. It is recommended a note be made in the subject's medical record that the subject is participating in the study.

Clinical study data will be collected using source document worksheets and eCRFs. A web-based electronic data capture system (EDC) will be used to record and manage study data. All eCRFs must be kept in good order and updated so they always reflect the latest observations on the subjects participating in the study.

The Investigator will sign the appropriate eCRF pages and source documentation. Pertinent eCRF corrections will be made electronically and signed electronically by the Investigator. An embedded audit trail will capture the date, time and user making entries and changes to the electronic data.

Because it is important to have proper data collection in a timely manner, it is recommended that the Investigator or designee complete eCRFs within 5 business days of data availability. When the monitor or designee requests additional data or clarification of data for the eCRF (queries), the request must be answered satisfactorily as soon as possible.

## 6.10.2 Data Security and Integrity

The Sponsor, auditors, and health authority inspectors (or their agents) will be given access to source data and documentation (e.g., medical charts/records, laboratory test results, printouts, videotapes, etc.) for source data verification, provided that subject confidentiality is maintained in accordance with local requirements.

The Investigator must maintain the primary records (source documents) of each subject's data. Examples of source documents are hospital records, office visit records, examining physician's finding or notes, consultant's written opinion or notes, laboratory reports, device label records, and worksheets that are used as the source.

# 7 STATISTICS & DATA ANALYSIS

## 7.1 SAMPLE SIZE

The sample size of the FlowTriever Arm is calculated using a two-stage group sequential design, where the FlowTriever Arm is expected to have a rate of in-hospital composite endpoint of all-cause mortality, bailout to an alternative thrombus removal strategy, clinical deterioration, and major bleeding (BARC 3b/3c/5a/5b definition) of 18%. The rate of the FlowTriever Arm composite endpoint is compared with the historical performance goal of 32%, based on meta-analysis results shown in Table 9. A one-sided binomial proportion's test with normal approximation is used against the historical performance goal with a power of 80% and a one-sided  $\alpha = 0.05$ ; O'Brien Fleming boundary was implemented where the first stage, or interim analysis, is planned at N = 50 subjects enrolled and consequently arriving at the second stage, or final analysis, with N = 71 subjects as shown in Table 8.

Analysis Stage	N	Z-score Threshold	P-value Threshold	FT Event proportion	Significant event number
Interim	50	-2.0311	0.0211	0.186	≤9.3
Final	71	-1.7116	0.0435	0.225	≤16.0

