## 7.4 ENDPOINT ANALYSIS

## 7.4.1 PRIMARY ENDPOINT ANALYSIS

The primary endpoint is the in-hospital composite endpoint of all-cause mortality, bailout to an alternative thrombus removal strategy, clinical deterioration, and major bleeding (BARC 3b/3c/5a/5b definition) from the FlowTriever Arm. The rate of the composite endpoint is expected to be 18% and compared with performance goal of 32%:

H0:  $P_S \ge Performance Goal_s versus H_A: P_S < Performance Goal_s$ 

where Ps is the proportion of subjects with in-hospital composite endpoint and Performance Goals is the performance goal of proportion of subjects with in-hospital composite endpoint derived from previous publications and expert opinions on subjects who were non-FlowTriever treatments.

The one-sided binomial's proportion test with normal approximation would be used at a one-sided  $\alpha$  = 0.05. Primary endpoint analysis can be carried out at interim analysis and/or final analysis stage.

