## 7.4.3 INTERIM ANALYSIS

The interim analysis population will be N = 50 enrolled subjects in the FlowTriever Arm with adjudicated in-hospital composite endpoint. Primary endpoint analysis method in **Section 7.4.1** will be used on the interim analysis population to decide whether the study should be stopped early due to achieving early decision rule based on the primary endpoint. The |z - score| threshold is 2.031, which translates to inhospital composite endpoint proportion being  $\leq$  0.186. Therefore, having  $\leq$  9 in-hospital composite endpoint events out of N = 50 may qualify for stopping the study early and conclude achieving significant difference from performance goal = 32% (see Table 9).

Secondary endpoint analysis may be conducted in a descriptive fashion without hypothesis testing, therefore not spending any Type I error ( $\alpha$ ).

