5.1. Sample Size

The sample size of the FlowTriever arm is calculated using a two-stage group sequential design, where the FlowTriever arm is expected to have a rate of in-hospital composite endpoint of all-cause mortality, bailout to an alternative thrombus removal strategy, clinical deterioration, and major bleeding (BARC 3b/3c/5a/5b definition) of 18%. The rate of the FlowTriever arm composite endpoint is compared with the historical performance goal of 32%, based on meta-analysis results shown in **Table** . A one-sided binomial proportion's test with normal approximation is used against the performance goal with a power of 80% and a one-sided α = 0.05; O'Brien Fleming boundary was implemented where the first stage, or interim analysis, is planned at N = 50 subjects enrolled and consequently arriving at the second stage, or final analysis, with N = 71 subjects as shown in **Table** .

Table 3: Sample Size 2-stage Group Sequential Design

Analysis Stage	N	Z-score Threshold	P-value Threshold	FT Event proportion	Significant event number
Interim	50	-2.0311	0.0211	0.186	≤9.3
Final	71	-1.7116	0.0435	0.225	≤16.0

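### The final success count printed as ≤16.0 of 71 conflicts with the plan's own z and p limits and raises exact one-sided type I error to 5.9%; the rule should read ≤15 of 71, judged by an exact test

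*Protocol*

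**What the plan says.** - **Test and goal.** Protocol section 7.1 specifies the test as "A one-sided binomial proportion's test with normal approximation is used against the historical performance goal with a power of 80" per cent, with the FlowTriever rate "compared with the historical performance goal of 32" per cent. SAP section 5.1 uses nearly the same words: "A one-sided binomial proportion's test with normal approximation is used against the performance goal with a power of 80" per cent. Protocol section 7.4.1 repeats it: "The one-sided binomial's proportion test with normal approximation would be used at a one-sided" level of 0.05.
- **Assumed rate.** "The rate of the composite endpoint is expected to be 18% and compared with performance goal of 32" per cent (Protocol section 7.4.1).
- **Looks.** "O'Brien Fleming boundary was implemented where the first stage, or interim analysis, is planned at N = 50 subjects enrolled", "consequently arriving at the second stage, or final analysis, with N = 71 subjects as shown in Table 8".
- **Printed limits (Protocol Table 8, SAP Table 3).** Interim, N = 50: z -2.0311, p 0.0211, proportion 0.186, count ≤9.3. Final, N = 71: z -1.7116, p 0.0435, proportion 0.225, count ≤16.0.
- **Counts in the text.** Protocol section 7.4.3 and SAP section 5.5 turn the interim 9.3 into a whole number: 9 or fewer "endpoint events out of N = 50 may qualify for stopping the study early and conclude achieving significant difference from performance goal = 32" per cent. Neither document states a whole-number count for the final look. Neither gives an exact test or an exact type I error, or says which column of the table governs.

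**The concern.** The study has one confirmatory hypothesis, tested in a single arm against a fixed goal, so one event can decide the result. A reader who takes the last column of the table at face value declares success at 16/71. A reader who computes z and compares it with the limit two columns to the left does not. If the count governs, success can be claimed when an exact interval still includes the 32% goal, and the stated one-sided 5% error rate is exceeded.

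**Working it through.** **Inputs.** Goal p0 = 0.32, expected rate p1 = 0.18, one-sided alpha 0.05, power 80%, O'Brien-Fleming boundary, looks at 50 and 71 (Protocol sections 7.1 and 7.4.1; SAP sections 5.1 and 5.3).

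**1. Reproducing the plan.** Take the standard error under the null, sqrt(p0(1 - p0)/n), and a two-look O'Brien-Fleming boundary. The unrounded N for 80% power is 70.41, rounded up to 71. The information fraction is 50/70.41 = 0.710. The final limit is -1.7116 and the interim limit is -1.7116/sqrt(0.710) = -2.031, as printed. Normal-theory power is 80.3%. As event counts:
- Interim: 0.32 - 2.0311 × sqrt(0.32 × 0.68/50) = 0.32 - 2.0311 × 0.06597 = 0.1860, and × 50 = 9.30 events.
- Final: 0.32 - 1.7116 × sqrt(0.32 × 0.68/71) = 0.32 - 1.7116 × 0.05536 = 0.2252, and × 71 = 15.99 events.

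The table shows 15.99 to one decimal, as 16.0. A whole number at or below 15.99 is 15, not 16.

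**2. The result 16/71 against the plan's own limits.** 16/71 = 0.22535. z = (0.22535 - 0.32)/0.05536 = -1.7097, short of -1.7116. The normal p is 0.0437, above 0.0435. At 15/71, z = -1.964 and p = 0.0248, inside both limits.

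**3. Exact binomial tail at p0 = 0.32.**

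| Result | Exact one-sided p | Nominal level |
|---|---|---|
| 9/50 | 0.0206 | 0.0211 |
| 15/71 | 0.0299 | 0.0435 |
| 16/71 | 0.0536 | 0.0435 |

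The exact (Clopper-Pearson) one-sided 95% upper limit for 16/71 is 32.19%.

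**4. Both looks together.** The exact rejection probability is P(X50 ≤ 9) + sum over x > 9 of P(X50 = x) × P(Y21 ≤ k - x), where Y21 is the number of events in the last 21 subjects and k the final count.

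| Rule | Exact type I error at 32% | Exact power at 18% |
|---|---|---|
| ≤9/50, ≤16/71 (printed counts) | 0.0206 + 0.0386 = 0.0591 | 87.8% |
| ≤9/50, ≤15/71 (strict z, or exact test) | 0.0206 + 0.0180 = 0.0386 | 81.7% |

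The components are rounded. If the interim is ignored and only the final count decides, type I error is 5.36% for ≤16 and 2.99% for ≤15, with power 87.3% and 80.2%.

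The difference between the rows is the chance that the trial passes the interim and ends on exactly 16/71: about 2.1% at a true rate of 32% and 6.1% at 18%.

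**5. If fewer than 71 are analysed.** With the interim at ≤9/50 and the final limit kept at z -1.7116 or exact p 0.0435:

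| Final N | Strict z: count, error, power | Exact test: count, error, power |
|---|---|---|
| 60 | ≤13, 5.65%, 82% | ≤12, 3.4%, 74% |
| 64 | ≤14, 5.5%, 84.0% | ≤13, 3.5%, 76.5% |
| 68 | ≤15, 5.4%, 85.4% | ≤14, 3.5%, 78.6% |

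At the other nine sizes from 60 to 71 the strict z rule has exact error between 3.9% and 4.9%. The exact test stays at or below 4.9% throughout. At N = 61 it is also one event stricter than z, although z holds there.

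**The case against.** The strongest reply is that the fault lies in a rounded table cell and not in the test. The text floors the interim 9.3 to 9. The same treatment of 15.99 gives 15, and the specified z test then rejects at ≤15/71 with exact error 3.9%. This stands as to cause. A reader might infer that the normal approximation fails to hold its level at this sample size. At 50 and 71 the documents do not support that: applied strictly, the z limits give the same counts, error and power as an exact test. The reply does not clear the plan, because both documents print ≤16.0, neither gives a whole-number final count, and nothing ranks the columns.

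Two further readings go too far.
- **That an exact test costs no power.** This is true against the strict z rule at 50 and 71. Against the printed count, exact power drops by 87.8 - 81.7 = 6.1 points.
- **That the interim could run on 49 or 53 subjects and breach its nominal level.** Protocol sections 5.2.1 and 7.4.3 fix it at the first 50 with adjudicated outcomes. Enrollment that continues during adjudication does not change which 50 are analysed. Even with 49 or 53, the overall exact error with ≤15/71 would be about 4.2% or 4.0%.

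It is also fair to say that a final analysis on fewer than 71 is not the plan. The final look is defined at 71, and Protocol section 6.1.6 expects no loss to follow-up. But section 6.8 allows termination for slow enrollment and SAP section 4 does not impute missing outcomes, so a smaller final number is possible. That gives secondary support for an exact test.

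**Conclusion.** The printed final count is wrong as a decision threshold. It contradicts the z and p limits in the same row, and used with ≤9/50 it gives an exact one-sided type I error of 5.9% against the stated 5%. The error is one event, at exactly 16/71. Read strictly, the z and p limits keep exact error at 3.9%, so the conclusion concerns the printed count and the missing rule on which limit governs. It does not show that the normal approximation is invalid at the planned sizes.

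The figures assume independent outcomes with a common event rate, analysis of exactly 50 and then 71 subjects, and success counted at either look. They take the 32% goal and the 18% expected rate as given.

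**What to change.** In Protocol Table 8 and SAP Table 3, replace ≤9.3 and ≤16.0 with ≤9 and ≤15, and state the final rule as ≤15/71 in the text of Protocol section 7.4.1 and SAP section 5.3. In both documents, base the decision on an exact one-sided binomial p-value at nominal 0.0211 (interim) and 0.0435 (final). Say that this p-value governs if the number analysed differs from plan, and report the exact upper confidence limit at the matching level.

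The cost is a wording change in both documents, with no change to sample size or interim timing. Exact power at 18% is 81.7% instead of the 87.8% that the printed count gives only by exceeding the stated error rate. If the final number falls short, the exact test holds 5% where strict z may not, but power at N = 60, 64 or 68 is then about 74% to 79%, below the planned 80%.

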5.5. Interim Analysis

The interim analysis population will be N = 50 enrolled subjects in the FlowTriever arm with adjudicated in-hospital composite endpoint. Primary endpoint analysis method in **Section 5.3** will be used on the interim analysis population to decide whether the study should be stopped early due to achieving early decision rule based on primary endpoint. The $\|z - score\|$ threshold is 2.031, which translates to inhospital composite endpoint proportion being ≤ 0.186 . Therefore, having ≤ 9 in-hospital composite endpoint events out of N = 50 patients may qualify for stopping the study early and conclude achieving significant difference from PG_S = 32% (see **Table**).

Secondary endpoint analysis may be conducted in a descriptive fashion without hypothesis testing, therefore not spending any Type I error (α).

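### The final success limit of 16 events in 71 fails the z and p limits in its own table row; counting 16 as a success puts the exact one-sided type I error at 5.9%

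*Protocol*

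**What the plan says.** Protocol 7.1 and SAP 5.1 describe a two-stage O'Brien-Fleming design "with a power of 80% and a one-sided α = 0.05". The test is the same at both looks: "A one-sided binomial proportion's test with normal approximation is used against the historical performance goal". The performance goal is 32% and the expected FlowTriever rate is 18%.

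Protocol Table 8 and SAP Table 3 print identical limits (columns: stage, N, z, p, proportion, significant event number):

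- "Interim 50 -2.0311 0.0211 0.186 ≤9.3"
- "Final 71 -1.7116 0.0435 0.225 ≤16.0"

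The interim limit of 9.3 is turned into a whole-number rule in the text. SAP 5.5 says "having ≤ 9 in-hospital composite endpoint events out of N = 50 patients may qualify for stopping the study early", and Protocol 7.4.3 agrees. Neither document has a matching sentence for the final analysis.

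Protocol 7.4.1 and SAP 5.3 set the test at a one-sided 0.05 and add "Primary endpoint analysis can be carried out at interim analysis and/or final analysis stage". They do not mention 0.0435 or any stage-specific limit.

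**The concern.** An event count is a whole number, so the final row has to say whether 16 events is a success. Its columns disagree: the event column admits 16, and the z and p columns reject it. An analyst programming from the event column, or from the plain 0.05 in the primary-analysis sections, would declare the performance goal met. An analyst programming from z or p would declare it not met.

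This row governs the only formal success test in the study. If the choice between 15 and 16 is still open once the data are known, it becomes a post hoc decision on the primary endpoint. The two choices also lie on opposite sides of the 5% error rate that the plan claims.

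**Working it through.** **Inputs.** Null rate p0 = 0.32 and expected rate 0.18 (Protocol 7.4.1, SAP 5.3). N = 50 and 71, with z limits -2.0311 and -1.7116 (Protocol Table 8, SAP Table 3). Interim success at 9 or fewer events (Protocol 7.4.3, SAP 5.5).

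**1. Reproduce the printed limits.** Limit proportion = p0 + z·√(p0(1 − p0)/N); limit events = N × that proportion; p = Φ(z).

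- Interim: 0.32 − 2.0311 × √(0.32 × 0.68/50) = 0.32 − 2.0311 × 0.06597 = 0.1860. Times 50 this is 9.300 events, and p = 0.0211. All match the table.
- Final: 0.32 − 1.7116 × √(0.32 × 0.68/71) = 0.32 − 1.7116 × 0.05536 = 0.22524. Times 71 this is 15.992 events, and p = 0.0435. The table shows 15.992 to one decimal, as 16.0.

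The table therefore uses the null variance. Under normal theory (correlation √(50/71) between looks) the two limits give an overall alpha of 5.01% and, with the null variance, power of 80.3%, so the design itself reproduces.

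**2. Test whole counts at the final look.** z = (x/71 − 0.32)/0.05536.

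| Events | Proportion | z | p | Meets z ≤ -1.7116 and p ≤ 0.0435? |
|---|---|---|---|---|
| 15 | 0.21127 | -1.9641 | 0.0248 | Yes |
| 16 | 0.22535 | -1.7097 | 0.0437 | No |

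A nominal 0.05 at the final look (z = -1.645) corresponds to 71 × (0.32 − 1.645 × 0.05536) = 16.25 events, so 16 would pass on that reading of Protocol 7.4.1 and SAP 5.3.

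**3. Exact error rate and power.** With b as the final limit:

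P(success) = P(X50 ≤ 9) + Σ over k ≥ 10 of P(X50 = k) × P(X21 ≤ b − k)

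Here X50 counts events in the first 50 subjects and X21 in the next 21.

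| Final limit b | Type I error at 32%: interim + final | Total | Power at 18% |
|---|---|---|---|
| 15 | 2.06% + 1.80% | 3.86% | 81.7% |
| 16 | 2.06% + 3.86% | 5.91% | 87.8% |

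(Totals are summed before rounding.) With a single look at 71 and no interim success allowed, the type I error is 2.99% for 15 and 5.36% for 16.

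**4. How often the ambiguity decides the result.** The probability of passing the interim without success and then finishing on exactly 16 is the difference between the two rows above. At 18% it is 87.8% − 81.7% = 6.1%. The same calculation gives 8.5% at 20% and 9.7% at 22%.

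**The case against.** The strongest reply is that the plan specifies a normal approximation, and on that scale admitting 16 costs almost nothing. Moving the final limit from -1.7116 to -1.7097 takes overall alpha from 5.01% to 5.03%. With the usable whole-number limits, 9/50 (z = -2.122) and 16/71 (z = -1.710), normal-theory alpha is 4.83%. The 5.91% comes from the exact binomial distribution, which neither document uses. The sponsor could then keep 16 and restate the limit as z = -1.7097, p = 0.0437.

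The arithmetic in that reply is right, but it does not settle the matter. The exact rate is the error rate the study would actually have, and it exceeds 5% with 16. The approximation's own printed z and p limits also reject 16, so keeping it means changing them.

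Three smaller points stand in part:

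- At three decimals 16/71 also displays as 0.225, so the conflict shows in the z and p columns rather than the proportion column.
- The 16.0 is ordinary one-decimal rounding of a continuous boundary, as 9.3 is. The fault is that it was left as a decision limit with no whole-number rule.
- The 0.05 in the primary-analysis sections is probably the overall design level, since the interim sections apply the same method with the 2.031 threshold. Those sections still do not say so or point to 0.0435.

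A test using the observed-rate variance would pass 16 (z = -1.909), but that variance does not reproduce the printed proportion and event limits. A recomputed classical O'Brien-Fleming boundary at 50/71 gives a final limit of -1.7108, which 16 events still misses.

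**Conclusion.** The concern holds, and the limit is wrong as written. The final event limit contradicts the z and p limits beside it, in both documents, and nothing elsewhere resolves the conflict. The numerical miss is tiny, but because counts are discrete it decides whether the whole 16-event outcome is a success. That outcome carries 2.05 percentage points of exact type I error (5.91% against 3.86%) and 6.1 points of power at 18%.

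Of the two candidates, only 15 satisfies the printed z and p limits, the stated 5% alpha and the stated 80% power together. These figures assume independent subjects with a common event rate, looks at exactly 50 and 71, and success declared at the interim with 9 or fewer events. Without the interim, 16 still exceeds 5% (5.36%).

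**What to change.** - In Protocol Table 8 and SAP Table 3, replace the event limits with whole numbers: at most 9 of 50 at the interim and at most 15 of 71 at the final analysis.
- In Protocol 7.4.1 and SAP 5.3, replace the bare one-sided 0.05 with the stage rules: interim success at ≤ 9/50 (z ≤ -2.0311); final success at ≤ 15/71 (z ≤ -1.7116, p ≤ 0.0435). State that 0.05 is the overall design level.
- Report the exact operating characteristics next to the table: overall one-sided type I error 3.9%, power 81.7% at an 18% rate.

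The cost is wording in four places and one fewer allowable event than the table now prints. No subjects are added and the stated power is kept. The change should be made before the final outcome data are known.
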